### **Hepatitis B and C Testing**

All subjects will be tested for the presence of the hepatitis B Virus (HBV) and hepatitis C Virus (HCV) at Screening. Subjects with hepatitis B (HBs Ag positive [+] or detected sensitivity on the HBV DNA PCR qualitative test for core antibodies (HBc Ab) positive subjects) or hepatitis C (HCV RNA detectable in any subject with anti-HCV Ab) will be excluded. Subjects who have been vaccinated against hepatitis B and are HBs Ab positive may be enrolled.

### **Clinical Laboratory Tests**

Blood samples will be obtained for the laboratory tests listed in [Table 2](#). Blood draws should be performed after all clinical assessments and questionnaires (IBDQ, etc.) and vital sign determinations are obtained during a visit.

A certified central laboratory will be utilized to process and provide results for the clinical laboratory tests. All abnormal laboratory tests that are considered clinically significant by the Investigator will be followed to a satisfactory resolution.

The central laboratory chosen for this study will provide instructions regarding the collection, processing and shipping of these samples.

The blood samples for serum chemistry tests should be collected following a minimum 8-hour fast, when possible. If a subject is not able to fast when necessary, due to unforeseen circumstances, the non-fasting status will be recorded in study source documentation. The fasting status will be recorded in the laboratory request, source document and CRF.

**Table 2. Clinical Laboratory Tests**

Hematology	Clinical Chemistry	Urinalysis a
Hematocrit	Blood Urea Nitrogen (BUN)	Specific gravity
Hemoglobin	Creatinine	Ketones
Red Blood Cell (RBC) count	Total bilirubin	pH
White Blood Cell (WBC) count	Albumin	Protein
Neutrophils	Aspartate aminotransferase (AST)	Glucose
Bands	Alanine aminotransferase (ALT)	Blood
Lymphocytes	Alkaline phosphatase	Nitrite
Monocytes	Creatine Phosphokinase (CPK)	Leukocytes
Basophils	Sodium	Microscopic Examination
Eosinophils	Potassium Chloride	
Platelet count (estimate not acceptable)	Bicarbonate	Other Laboratory Tests
Reticulocyte count	Calcium	Serum pregnancy test
	Inorganic phosphorus	Urine pregnancy test
	Uric acid	High sensitivity C-reactive protein (hs-CRP)
	Cholesterol	Hbs Ag
	LDL cholesterol	HBs Ab
	HDL cholesterol	HBc Ab
	Total protein	HBV DNA PCR reflex only
	Glucose	HCV Ab
	Triglycerides	HCV RNA reflex only
	Chloride	PPD
		QuantiFERON-TB Gold
	Stool Samples Collected	Pharmacodynamic biomarkers
	C. difficile toxin	Pharmacokinetic
	Fecal calprotectin	
Additional Samples Collected (Optional)		
Pharmacogenetic mRNA		
Serologic markers		
Biopsy for gene expression		

a. Microscopic urinalysis will be analyzed when dipstick results are abnormal.

### Urinalysis

Urine samples will be obtained and sent to the central laboratory for the tests listed in **Table 2**. Microscopic urinalysis will only be performed by the central laboratory if the

dipstick UA results are abnormal, where abnormal is defined as leukocytes, nitrite, ketone, protein, blood or glucose value of greater than a trace.

### **Other Laboratory Assessments**

#### **hs-CRP**

Blood samples for high-sensitivity C-reactive protein (hs-CRP) will be obtained. Blood draws should be performed after all clinical assessments, questionnaires (IBDQ, etc.), and vital sign determinations are obtained. The hs-CRP results from Week 2 through Week 16 will be blinded to sites/sponsor. The hs-CRP results after Week 16 will be un-blinded.

hs-CRP will be performed by Central Lab. However, for the purpose of evaluating Inadequate Response criteria, hs-CRP can also be done at local lab. At Week 20, since the Week 16 hs-CRP will still be blinded, the hs-CRP performed by the local lab or the Week 20 Central Lab result will be used for the assessment of Inadequate Response.

### **Stool Samples Collected**

#### **Fecal Calprotectin**

Fecal calprotectin will be performed for all subjects as indicated in [Table 1](#). Subjects will be asked to provide a stool sample, subjects will be sent home with instructions and a stool sample supplies (supplies will be provided).

The fecal calprotectin results will remain blinded to Investigator, study site personnel and the subject throughout the study.

All stool samples should be collected before any bowel preparation for endoscopy is started. The central laboratory will be utilized to process and provide results for these laboratory tests.

The stool sample collected during the Screening Period will be used for the Baseline assessment (prior to receiving study drug).

***C. Difficile***

During the Screening Period a stool sample will be collected and sent to the central laboratory for testing. The sample will be assessed for the presence of *C. difficile* toxin.

The sample must be shipped to the central laboratory using dry ice. Additional information is available in the Investigator Manual provided by the central laboratory.

Subjects who are positive for *C. difficile* toxin may be treated appropriately and re-screened.

**CDAI**

A CDAI will be calculated from a subject diary, physical exam, and appropriate laboratory values at all study visits beginning at Screening. The Screening Period will be a minimum of 7 days but will not exceed 35 days. The CDAI calculated during Screening will serve as the Baseline CDAI.

For calculation of CDAI scores, beginning with the Week 2 through Week 52, the CDAI scores must be calculated using a hematocrit value from the preceding visit laboratory work.

CDAI at Visit	Hematocrit Value Utilized
Week 2	Baseline
Week 4	Week 2
Week 8	Week 4
Week 12	Week 8
Week 16	Week 12
Week 20	Week 16
Week 28	Week 20
Week 36	Week 28
Week 44	Week 36
Week 52	Week 44

For calculating CDAI, to answer questions one (1) through three (3), entries from the 7 days prior to the day of study visit should be used as recorded by the subject from the diary.

Diary entries should not be included in the 7 days evaluated prior to the visit if: (1) the day the subject received medication for bowel preparation prior to endoscopy, (2) the day the subject underwent an endoscopy, and (3) 2 days following the endoscopy. Earlier diary entries will be used accordingly in order to provide the most recent data for 7 days prior to the respective study visit.

For the CDAI questions regarding presence of anal fistulas and other fistulas, all fistulas detectable on physical examination (draining and non-draining) should be captured on the CDAI and calculated into the CDAI score.

When completing question five (5) ("Taking Lomotil/Imodium/Loperamide/opiates for diarrhea, 0 = no, 1 = yes") on the CDAI, "no" should be answered if a subject is taking an opiate(s) solely for pain.

For question seven (7), hematocrit results from central laboratory will be used for the CDAI calculation. If the hematocrit value contains more than one decimal point, the rounding will be allowed to the tenths decimal (e.g., Hematocrit value 33.44 will be captured as 33.4, Hematocrit value of 33.45 will be captured as 33.5). The Hematocrit values either prior to completing the calculation or at the subtotal box 7 of the CDAI should not be rounded to a whole number.

The height obtained at Screening should be used when selecting the standard weight in [Appendix E](#), and this standard weight should be used for calculating every CDAI throughout subject participation in the study.

Standard height is calculated by using the height obtained at Screening (without shoes) plus one inch.

If the body weight obtained at the time of assessment is not captured in kilograms (kg), then when converting into kgs, rounding should occur using the second digit after the decimal (also known as the hundredth place) where if the number is 0 – 4 then keep the first digit after the decimal (also known as the tenth place) unchanged. If the second digit after the decimal is 5 – 9 then round up the first digit after the decimal (e.g., 90.246 would be captured as 90.2, 97.687 would be captured as 97.7).

The subtotal of box 8 should not be rounded to a whole number. The calculation of the CDAI score is in [Appendix D](#).

## **Outcomes and Questionnaires**

- IBDQ – Inflammatory Bowel Disease Questionnaire (IBDQ) will be completed at the time points indicated in [Table 1](#).
- WPAI – Work Productivity and Activity Impairment Questionnaire (WPAI) will be completed at the time points indicated in [Table 1](#). The data in the subject completed questionnaire will be transferred to the appropriate eCRF (Electronic Case Report Form) by the site personnel at each study visit ([Appendix C](#)).
- EQ-5D – European Quality of Life 5 Dimensions, a standardized questionnaire for use as a measure of health outcome will be completed at the time points indicated in [Table 1](#).
- Abdominal Pain Rating Scale (0 – 10 Scale) ([Appendix I](#)).

## **Corticosteroid Taper**

At Week 2, subjects who are on prednisone or budesonide must have their corticosteroid dose tapered according to the following proposed schedule or based on Investigators' discretion:

---

	Dose	Rate
Prednisone (or equivalent)	> 10 mg/day	5 mg/day/week
	≤ 10 mg/day	2.5 mg/day/week
Budesonide	≤ 9 mg/day	3 mg/day/week

If a subject should experience an inadequate response during the corticosteroid taper, the subject may have their corticosteroid dose increased, per the investigator's discretion, up to and beyond the dose used at Baseline. Subjects in whom the maximum steroid dose exceeds the dose used at Baseline will be considered non-responders and will be censored for efficacy assessments from that point forward through the end of the study. These subjects will continue to be evaluated in the safety population.

### **Subject Diary**

Subjects will be dispensed an electronic diary at Screening and will be trained on how to complete the diary by site staff during the Screening Visit. All subjects should complete their subject diary on a daily basis throughout the entire study. The diary will be reviewed by site personnel with the subject at each visit and collected at the Final/ET Visit.

The dosing records will be reviewed and verified for compliance at each visit by the research personnel at the study center and reinforced if necessary. All relevant dosing information will be retained by the study coordinator and transcribed into the eCRF. Additionally, any discernible departure from the protocol regarding study drug administration will be recorded on the source documents and in the appropriate drug accountability form.

### **Study Drug Dispensing/Administration**

Study drug will be dispensed to subjects beginning at Baseline and at all study visits through Week 52. No study medication will be dispensed at Week 52.

(Refer to Section [5.5](#) for additional information.)

## **Endoscopy**

An endoscopy will be performed on the following visits:

- During Screening\*
- Week 12 or Week 16
- Week 52/Early Termination

For those subjects who discontinue the study between Weeks 8 and 12 the endoscopy performed at the Early Termination Visit will be used as the Week 12 endoscopy result. An endoscopy will not be performed if a subject discontinues the study prior to Week 8.

In addition, for those subjects who discontinue the study during the extension phase, an endoscopy will not be performed if a subject discontinues the study prior to Week 28.

\* An endoscopy performed before the Screening visit, independently of the study, may be used as the Screening endoscopy, with the approval of the AbbVie Study Designated Physician, if the following conditions are met:

1. biopsy confirmation of the diagnosis is available according to section "Biopsy During Endoscopy" below.
2. the endoscopy took place within 15 days of Screening Visit.
3. the endoscopy was recorded in a video format as the endoscopic eligibility will be determined by the central reviewers. The same endoscopist, where possible, should perform all endoscopies.

An ileo-colonoscopy will be performed and recorded at the site in a video format and will be reviewed by a central reviewer who is blinded to the therapy, during the Screening Period (or within 15 days of the Screening Visit), Week 12 or Week 16 and the Week 52/ET Visit. There will be a window of  $\pm$  7 days to conduct the ileocolonoscopy. This window may be extended as necessary after consultation with the AbbVie Study Designated Physician in case of external, not subject-related circumstances

(e.g., scheduling conflict). The central reviewer will evaluate the data and provide the endoscopy subscore for calculating the Simplified Endoscopic Score (SES CD). Discrepancies between the central reviewer and the site endoscopist regarding a subject's score will be finally judged through adjudication by a second central reviewer. The adjudicator will not provide an assessment but will select the assessment with whom he/she agrees. The adjudicator's assessment will be considered final. Endoscopic eligibility will be determined by the central reviewers. If, in the opinion of the Investigator, the Screening endoscopy does not indicate the SES-CD criteria confirming study eligibility, the subject should be screen-failed and the video should not be sent for central review.

The same endoscopist should perform all endoscopies for an individual subject throughout the study. In addition, where possible, the investigator or subinvestigator should be the endoscopist for the study.

The endoscopy during the Screening Period (or endoscopy performed within 15 days of the Screening Visit), Week 12 or Week 16 and Week 52/ET will be used to provide the endoscopy subscores for calculating the Simplified Endoscopic Score (SES CD) at Screening, Week 12 or Week 16 and Week 52/ET, respectively, refer to [Appendix F](#).

The endoscopy subscores by segment will be noted in the subject's source documents and in the database but the central reviewer's endoscopy subscore will be used for the efficacy analyses.

For stratification at Week 16 re-randomization, the local reading (at Week 12 or Week 16) will be compared with the baseline central reading in order to determine response status.

### **Biopsy During Endoscopy**

Appropriate documentation of biopsy results consistent with the diagnosis of CD, in the assessment of the Investigator, must be available in order to confirm the subject's eligibility for the study. If this documentation is not available a diagnostic biopsy from the most affected area of the colon must be performed during the Screening endoscopy

and read by a qualified local pathologist and the results reviewed by the Investigator. Biopsies to rule out dysplasia and colon cancer may be taken per the Investigator's discretion during any endoscopy performed during this study and evaluated by the local pathologist.

If any biopsy sample(s) are obtained, it should also be recorded on the video.

Any biopsy sample(s) will be collected from the respective bowel segment during the withdrawal of the endoscope and after sufficient recording for the central reader to calculate the SES-CD.

The signed pathology report will be monitored by the responsible Clinical Research Associate (CRA) and kept with the subject's source documents onsite. Subjects should not be enrolled if colon dysplasia or colon cancer is discovered at Screening endoscopy or endoscopy performed within 15 days of the Screening Visit.

If a diagnosis of colon dysplasia or colon cancer is discovered during any subsequent endoscopic evaluation during the course of the study, the findings should be recorded as an adverse event and the subject should be discontinued from the study.

### **5.3.1.2        Blood Samples for Pharmacogenetic Analysis**

An optional whole blood sample for DNA isolation will be collected on Baseline Visit from each subject who consents to provide samples for pharmacogenetic analysis. The procedure for obtaining and documenting informed consent is discussed in Section 9.3.

The sample collection tubes will minimally be labeled with "PG-DNA," protocol number, subject number and the study day. Samples will be shipped frozen to AbbVie or a designated laboratory for DNA extraction and long-term storage. Instructions for the preparation and shipment of pharmacogenetic samples will be provided outside of this protocol.

AbbVie will store the DNA samples in a secure storage space with adequate measures to protect confidentiality. The samples will be retained while research on ABT-494 (or drugs of this class) continues but no longer than 20 years after study completion (where allowed by local guidelines).

#### **5.3.1.3      Collection and Handling of In Vivo Pharmacodynamic Biomarker Variables**

Serum samples will be collected at time points specified in [Table 1](#) to assess JAK activity effects on certain lymphocyte subsets including T (CD4+ and CD8+), B, NK cell subsets, reticulocyte and other cell types.

Instructions on preparation and shipment of pharmacodynamic (in vivo biomarkers) samples will be provided by a certified laboratory or the sponsor outside this protocol. In vivo biomarkers will be assayed using a validated method under the supervision of the Bioanalysis Department at AbbVie.

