**Methodology (Continued):**

In addition, the following will be conducted during the study as noted below:

- Results of QoL and work productivity questionnaires (IBDQ, EQ-5D, WPAI) at Baseline, Week 8, and Weeks 16, and 52/Early Termination.
- Serum for measurement of ABT-494 concentrations at Week 2, Week 4, Week 8, Week 12, Week 16, Week 20, Week 28, Week 36, Week 44 and Week 52/Early Termination.
- A serum pharmacodynamics sample will be drawn at Baseline, Week 8, Week 16 and Week 52/Early Termination.
- Endoscopic evaluations using SES-CD, confirmed by central reader, will be done during Screening, Week 12 or Week 16, and Week 52/Early Termination. The Week 12 or Week 16 endoscopy will not be performed if a subject discontinues the study prior to Week 8. In addition, if a subject prematurely discontinues from the extension phase of the study before or at Week 28, the endoscopy at the Early Termination Visit will not be required. Biopsy to confirm diagnosis (during Screening) or to rule out dysplasia/malignancy may be performed during the same time points as the endoscopy specified above.
- Stool samples for measurement of fecal calprotectin during Screening, Week 4, Week 16, Week 28 and Week 52/Early Termination Visit and at Unscheduled Visits resulting in dose change.
- Results of Abdominal Pain Rating Scale (0 – 10 scale) evaluating Abdominal Pain Intensity will be collected at Baseline, Week 12 and Week 16. (Note: this is an additional pain scale to the daily pain assessment that is collected as part of the CDAI).
- An optional serum for evaluation of biomarkers at Baseline and Week 16.
- An optional whole blood mRNA sample will be drawn at Baseline and Week 16.
- An optional whole blood pharmacogenetic sample will be drawn at Baseline.
- An optional biopsy for Gene expression sub-study will be collected during colonoscopy at/during Screening, and at Week 12/16 for approximately 80 subjects in the study.

Throughout the study, subjects will only be allowed to change the dosage of CD-specific concomitant medications as specified below:

- Starting at Week 2, subjects who are taking corticosteroids at Baseline must have their steroid dose tapered.
- Aminosalicylates dose must remain unchanged for the entire study period.
- MTX dose must remain unchanged for the entire study period.

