### **8.1.9            Statistical Analysis of Biomarker Data**

Summary statistics for the pharmacodynamic biomarkers and disease response biomarkers at Baseline and post-treatment time points, in addition to change from Baseline at each time will be provided; this will include mean, standard deviation, median, quartiles, and range for each group. Appropriate graphical visualizations such as association of each biomarker to the relevant efficacy endpoints, pairwise correlations between biomarkers,

trellis/3D plots that condition on Baseline factors, etc., will be provided. The pharmacodynamic effect of each biomarker between the placebo and ABT-494 treatment groups will be evaluated via a mixed-effects model with Treatment, Time and Treatment  $\times$  Time interaction as fixed-effects, the corresponding Baseline score as a covariate, and "subjects nested within the treatment group" as a random-effect. Other Baseline variables such as age, weight, etc., may be considered as appropriate. For biomarkers identified to have significant overall treatment effect via this mixed-effects model analysis, dose response models with the biomarker as a continuous response will be explored. In addition to the above analyses of biomarkers individually, the effect of certain combination of biomarkers on the treatment groups may be explored.

The association of biomarkers to the efficacy and safety endpoints will be explored for each biomarker one at a time, and also for combinations of biomarkers via some multivariate predictive modeling algorithms. Pairwise correlations and graphical summaries will be provided. Optimal multivariate combinations of biomarkers that associate with efficacy endpoints, subject response/non-response (with respect to appropriate clinical endpoints), and also with safety endpoints will be explored via a variety of statistical predictive modeling algorithms. Also cut-points for individual biomarkers and optimal combinations of biomarkers that differentiate the subject response with respect to efficacy/safety endpoints will be explored. The significance of these multivariate combinations of biomarkers will be assessed via at least 20 iterations of 5-fold cross-validation.

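### The protocol specifies serum for the pharmacodynamic sample, but the lymphocyte subsets that sample is meant to measure are cells and cannot be counted in serum

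*Protocol*

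**What the plan says.** Protocol Section 5.3.1.3 gives the sample and its purpose in one sentence. It opens "Serum samples will be collected at time points specified in" Table 1, and the purpose is "to assess JAK activity effects on certain lymphocyte subsets including T (CD4+ and CD8+), B, NK cell subsets, reticulocyte and other cell types". The synopsis (Section 1.2, Methodology) names the same matrix: "A serum pharmacodynamics sample will be drawn at Baseline, Week 8, Week 16 and Week 52/Early Termination". Tables 1 and 2 list the pharmacodynamic biomarkers without naming a matrix.

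Section 5.3.1.3 then leaves handling to another document: "Instructions on preparation and shipment of pharmacodynamic (in vivo biomarkers) samples will be provided by a certified laboratory or the sponsor outside this protocol".

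Section 8.1.9 states how the results will be used: "The pharmacodynamic effect of each biomarker between the placebo and ABT-494 treatment groups will be evaluated via a mixed-effects model". Biomarkers with a significant overall treatment effect then go into exploratory dose-response models, and associations with efficacy and safety are also explored. Under Section 8.1.10, pharmacodynamic data enter the first interim analysis and, if it is done, the second.

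**The concern.** The sample and the analytes do not match. Every analyte named in Section 5.3.1.3 is a cell population, and serum is what remains once the cells have been removed by clotting and centrifugation. A laboratory that receives only serum cannot report CD4+, CD8+, B or NK counts.

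The NK count carries the most weight. The Introduction (Section 3.0) argues that the drug's low activity against JAK3 could limit the fall in NK cells seen with tofacitinib, which may have contributed to viral infection and in particular to herpes zoster reactivation. The subset panel is the only scheduled measurement that bears directly on the NK part of that argument. A sample drawn in the wrong tube cannot be recovered later, because the visit has passed.

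**Working it through.** The plan gives no figure to reproduce. The check sets matrix against analyte, looks for another source of the counts, and then asks what the analysis would receive. It relies on one general fact that the documents do not state: serum contains no cells.

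**1. Matrix against analyte**

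| Analyte (Section 5.3.1.3) | Type | Countable in serum? | Other source in Table 2? |
|---|---|---|---|
| CD4+ and CD8+ T cells | cells | no | no |
| B cells | cells | no | no |
| NK cells | cells | no | no |
| Reticulocytes | cells | no | yes, hematology panel |
| Other cell types | cells, unnamed | no | cannot be judged |

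Table 2 lists "Reticulocyte count" and total lymphocytes under hematology, and Table 1 schedules hematology at every visit. The panel has no subset counts. The optional samples (DNA, mRNA, serologic markers, biopsy for gene expression) are not described as giving any.

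**2. Is the word deliberate?** The evidence points both ways.
- The protocol names whole blood where it wants it: "An optional whole blood mRNA sample will be drawn at Baseline and Week 16", and likewise the DNA sample in Section 5.3.1.2. Against that background a reader would take serum literally.
- In the same synopsis list the drug assay is described as "Serum for measurement of ABT-494 concentrations at Week 2", whereas Sections 5.3.2.1 to 5.3.2.3 say plasma. So the synopsis uses the word loosely at least once.

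**3. What the analysis would receive if the text is followed literally**
- Scheduled draws per subject: Baseline, Week 8, Week 16, Week 52/Early Termination = 4.
- Planned ceiling: 4 × 210 = 840 draws.
- After Week 16 all re-randomized subjects receive ABT-494, so a comparison with concurrent placebo can use only Baseline, Week 8 and Week 16: 3 × 210 = 630 draws.
- Subset results obtainable from serum: 0 of 840, and 0 of the 630 that bear on the placebo comparison.

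Both totals assume exactly 210 subjects and no drop-out, so the actual numbers would be lower. The zero does not depend on them.

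**4. What if the laboratory instructions differ?** Section 5.3.1.3 defers preparation and shipment, but it states the matrix itself. If the instructions repeat serum, no subset counts can be obtained. If they call for whole blood, the counts can be obtained but the instructions contradict the protocol, and Section 7.0 does not permit planned departures from it. The text needs correcting in either case.

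**The case against.** The strongest reply is that this is a slip of terminology. Sites take their tube and preparation steps from the laboratory instructions, which are outside the protocol and not available here. Section 5.3.1.3 also requires a validated assay method, and a validated subset count would not be run on serum. The serum/plasma discrepancy for the drug assay supports the view that the word was used carelessly.

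Much of this stands, and it rules out several stronger readings that a reader might infer.
- **That the subset data will be, or were, lost.** The documents do not show this. The loss follows only if the text is applied literally.
- **That reticulocyte data are lost too.** They are in routine hematology at every visit.
- **That trial endpoints are compromised.** The subsets are not among the primary, secondary or additional efficacy variables (Sections 5.3.3.1 to 5.3.3.3) or the safety variables named in Section 5.3.4, and neither SAP specifies a subset analysis. They are pharmacodynamic variables.
- **That the safety question behind the NK rationale goes unexamined.** Both SAPs (Section 11.2.2) track herpes zoster and opportunistic infection as adverse events of special interest. What has no substitute is the NK count itself.
- **That Section 8.1.9 as a whole depends on this panel.** It covers pharmacodynamic and disease-response biomarkers generally, and its dose-response step is exploratory.

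The reply does not remove the error. The protocol states the matrix, states it in two places, and nothing elsewhere in the protocol corrects it.

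**Conclusion.** The protocol is wrong as written: the synopsis and Section 5.3.1.3 prescribe a sample that cannot yield the lymphocyte subsets it is drawn for, and no other sample in Table 2 supplies them. Followed literally, the Section 8.1.9 comparison would have no CD4+, CD8+, B or NK results at any scheduled visit, including the only planned NK measurement.

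The consequence is limited to that panel and is conditional. It assumes that the laboratory instructions follow the protocol's stated matrix, which cannot be checked here. The co-primary analyses, the sample size and the power do not depend on it. Confidence is high that the wording is wrong; the documents do not establish that data would in fact be missing.

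**What to change.** In the synopsis and Section 5.3.1.3:
- specify an anticoagulated whole-blood sample for the lymphocyte-subset panel in place of serum;
- keep a serum sample only for soluble pharmacodynamic analytes, if there are any, and name them;
- state that reticulocytes come from the Table 2 hematology panel.

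Then check the laboratory instructions against the corrected text and align the two. Shipping and stability details can stay in those instructions.

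The cost is a wording change in two places, a check of the laboratory instructions and, if serum tubes are in use, a different tube at the same venipuncture. No extra visit or procedure is needed, and no efficacy analysis changes.
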